# Heated Humidified Breathing Circuit Rewarming in Hypothermic Patients after Cardiopulmonary Bypass

## Purpose of the Study

Our primary objective is to assess whether use of Heated Humidified breathing circuits (HHBC) decreases time to normothermia ( $\geq 36.5$  °C).

Our secondary objectives are to assess whether use of HHBC shorten time to extubation, improve coagulopathy, decrease bleeding, and metabolic derangements seen with hypothermia.

We propose the hypothesis that: Rewarming hypothermic patients ( $\leq 35$  °C) admitted to the CTICU following cardiac surgery with CPB, using HHBC in addition to conventional forced air warming blankets will shorten time to normothermia.

## Background & Significance

To reduce the rising cost of cardiac operations, researchers have studied early extubation as a means to shorten ICU length of stay, and favorably influence patients' health outcomes. In the process, various nursing ICU protocols have been developed to facilitate the expedient tracheal extubation of patients, taking into account hemodynamic status, mediastinal drainage, urine output, patient temperature (rewarming from induced hypothermia), and other factors.

Hypothermia on admission to the ICU following CPB is common. Cooling and rewarming during CPB and takes considerable time and contributes to the post-procedural coagulopathy and physiologic perturbations.

Rewarming in the postoperative period after hypothermic CPB is often associated with hemodynamic and ventilatory instability. Temperature changes, PaCO2 values, and mechanical ventilation were observed for the first 12 hours in the ICU in 73 patients who had undergone cardiac surgery with hypothermic CPB. Mean rectal temperature increased from 34.7 to 38.3 degrees C over the first 8 hr after admission to the ICU. The temperature curve was sigmoid rather than linear, and the most rapid rate of temperature increase occurred 2-4 hours after admission. During rewarming, the most common abnormality of PaCO2 on mechanical ventilation was acute respiratory acidosis (PaCO2 greater than 45 mmHg, pH less than 7.35), which occurred in 42% of patients.

After disconnecting from CPB the body is allowed to self-equilibrate. The normal vasoconstriction response is impaired by the administered anaesthesia. Hence, heat distribution takes place from the warm core to the colder periphery. This causes an afterdrop: a decrease in the temperature of the core organs. After-drop may contribute to post-operative complications of hypothermia such as shivering, coagulopathy, increased myocardial stress, increased wound infections, metabolic acidosis, delayed extubation and prolonged ICU length of stay.

The current standard of rewarming patients in the ICU is to use forced air heating blankets. Forced-air blankets reduce the core temperature afterdrop by 60%. However, heat-balance data indicate that this reduction resulted primarily because forced-air heating prevented the typical decrease in body heat content after discontinuation of CPB, rather than by reducing redistribution. They do not lead to clinical relevant changes in deep thigh temperature, or toe perfusion. The extra heat especially favors core temperature. This is underlined by the decrease in postoperative leg blood flow, suggesting that the majority of the warmed blood leaving the heart flows to core organs and not to the periphery.

A recent Cochrane review showed that active warming, particularly forced air warming, appears to offer a clinically important reduction in mean time taken to achieve normothermia (normal body temperature between 36°C and 37.5°C) in patients with postoperative hypothermia. However, high-quality evidence on other important clinical outcomes is lacking; therefore it is unclear whether active warming offers other benefits or harms. High-quality evidence on other warming methods is also lacking; therefore it is unclear whether other rewarming methods are effective in reversing postoperative hypothermia.

Regarding HHBC, Hyungseok et al recently showed that a heated humidifier is more effective in preventing intraoperative core temperature decrease in elderly patients than a heat moisture exchanger alone. Sooyong et al showed that a decrease in core temperature from anesthetic induction to 120 minutes after induction was lower in the HHBC group in patients undergoing hip arthroscopy. Park et al showed that HHBC influences heat redistribution in early period of thyroid surgery and can lessen the magnitude of the decrease in core body temperature. Frank et al showed that the delivery of warmed, humidified O2 via nasal canula accelerates core rewarming rate by approximately two-fold in mildly hypothermic postoperative patients. A recent fellow QI project used HHBC during rewarming of patients in the operating room following DHCA procedures found that it significantly attenuated the temperature afterdrop upon separation from CPB when compared to standard airway circuits.

## **Design & Procedures**

Hypothermia ( $\leq 35$  °C) after cardiac surgery using CPB is not uncommon. To avoid complications associated with hypothermia, and due to absence of shivering when patient is sedated, and harmful effects of shivering when patient is awake, clinicians resort to active warming devices. Forced air warming devices are the most commonly utilized, but occasionally heated humidified breathing circuits are used as well. We plan to use both warming devices on study patients, and compare them with a historical cohort that has used forced air warming device only.

On admission to CTICU, if temperature  $\leq 35$  °C, we will attempt to recruit the patient. Patients are intubated and sedated on admission to the CTICU after cardiac surgery, so informed consent will be obtained from the patient's next of kin or power of attorney. After consent is obtained, the clinical provider will ask the patient's nurse to place a lower body forced air warming device and set to 38 °C, and ask the respiratory therapist to set up and connect a heated humidified breathing circuit.

Admission temperature and other vital signs will be recorded per CTICU standards. Other patient management decisions (ie medication changes, laboratory assessments...etc) per direction of ICU providers. Core temperature and location (esophageal, nasopharyngeal, bladder, rectal, blood) will be recorded every 15-30 minutes until normothermia reached (36.5 °C), then record per CTICU standard. Record active warming methods in nursing flow sheets (i.e. Forced air warming blanket and heated humidified breathing circuit). Record other vital signs, medications, extubation time, hourly chest tube output, and patient data per unit policy. Alert Respiratory therapy once normothermia (36.5 °C) has been achieved for discontinuation of HHBC.

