#### Exclusion Criteria:

Patients admitted to ICU on ECMO support.

For the retrospective part of the study:

We will be matching the 14 prospective patients who received both ANAPOD and forced warm air with 28 retrospective ones who presented with hypothermia that were treated with forced warm air alone without ANAPOD. Criteria should include:

- Hypothermic Patients (Temp < 35C) undergoing cardiac surgery under CPB who received forced warm air alone.
- Temp at time of ANAPOD application would be our reference point.
- Type of surgery
- Patient's BMI
- Deep hypothermic arrest

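### Forced air, the standard care, is ordered only in the step after surrogate consent; any resulting difference in its start from controls would be counted as an HHBC effect

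*Combined protocol and SAP*

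**What the plan says.** Purpose of the Study states the hypothesis as "using HHBC in addition to conventional forced air warming blankets will shorten time to normothermia". Background & Significance gives the place of forced air in usual care: "The current standard of rewarming patients in the ICU is to use forced air heating blankets". It also cites a review in which "forced air warming, appears to offer a clinically important reduction in mean time taken to achieve normothermia".

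Design & Procedures sets the order of events in treated patients. Next of kin or power of attorney is approached after CTICU admission. The next step begins "After consent is obtained, the clinical provider will ask", and in it the provider asks the "nurse to place a lower body forced air warming device and set to 38" °C and asks the respiratory therapist to connect HHBC. The same section says "Record active warming methods in nursing flow sheets".

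The retrospective part, under Exclusion Criteria, describes controls as "Hypothermic Patients (Temp < 35C) undergoing cardiac surgery under CPB who received forced warm air alone". The other items listed are temperature at ANAPOD application (named as the reference point), type of surgery, BMI and deep hypothermic arrest. The start of forced air is not listed.

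Risk/Benefit Assessment says that a patient whose representative declines will be actively rewarmed with forced air only. It does not say when that begins.

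Data Analysis & Statistical Considerations plans a two-group t-test or Wilcoxon rank sum test and expects no adjustment beyond the matching. It states expected times to normothermia, 45 minutes to 6 hours, counted from ICU admission.

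**The concern.** The comparison isolates HHBC only if forced air is comparable in the two groups. As written, a step that can postpone forced air exists in one group alone: treated patients pass through surrogate consent before the request is made, and controls had no such step. By the protocol's own account forced air appears to shorten time to normothermia, which is the primary endpoint. Neither the matching list nor the planned test deals with when it began, so a net difference in start would enter the estimate as if HHBC had caused it.

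The bias could run either way. Later forced air in treated patients would hide a benefit; later forced air in controls would create one.

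The time origin adds to the uncertainty. Counted from admission, a consent wait lengthens treated times. Counted from ANAPOD application, treated patients may begin forced air near time zero while controls may already be on it, and the net direction is unclear. Controls never had an ANAPOD application, so their corresponding moment is undefined.

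There is also a care issue: followed literally, the text makes standard warming of a hypothermic patient wait for research consent.

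**Working it through.** **Inputs from Data Analysis & Statistical Considerations:** 14 treated and 28 control patients, SD 1.3 h, target difference 1.25 h, alpha 0.05, stated power 82%. Sidedness is not stated; two-sided is assumed because it reproduces the stated figure (one-sided gives 89.3%).

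**Reproducing the plan's figure.** SE = 1.3 × √(1/14 + 1/28) = 0.4255 h. Degrees of freedom = 14 + 28 − 2 = 40. Noncentrality = 1.25 / 0.4255 = 2.94. Two-sided power from the noncentral t is 81.8%, which agrees with 82%. The sample-size arithmetic is not at issue. The smallest significant observed difference is about 0.86 h.

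**Effect of an assumed shift.** Let b be a net between-group difference in time to normothermia caused by forced-air timing. The documents give no value for b, so the values below are assumptions. Against HHBC, the difference being tested is 1.25 − b. In favour of HHBC with no true effect, it is b. Each is divided by 0.4255 to give the noncentrality.

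| Assumed b (h) | Power if b runs against HHBC, true effect 1.25 h | Chance of p < 0.05 if b favours HHBC, no true effect |
|---|---|---|
| 0 | 82% | 5% |
| 0.125 | 73% (difference 1.125 h) | 6% |
| 0.25 | 63% (difference 1.00 h) | 9% |
| 0.5 | 41% (difference 0.75 h) | 21% |

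A shift of 0.5 h is 0.5 / 1.25 = 40% of the target difference.

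**From start time to endpoint.** A difference in start is not the same as a shift in the endpoint: b = start difference × the fraction that carries through. For an assumed net start difference of 30 minutes, b = 0.5 × 0.25 = 0.125 h, 0.5 × 0.5 = 0.25 h, or 0.5 × 1.0 = 0.5 h. The documents give neither factor. Background & Significance reports a series in which "the most rapid rate of temperature increase occurred 2-4 hours after admission", with the warming method not stated, so full carry-through should not be presumed.

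**The case against.** The strongest reply is that the text gives an order of requests and nowhere says forced air is withheld until consent. Forced air is the ICU standard and is used even after refusal, so it may well start on arrival in practice. This stands: the documents show an ambiguity and a possible delay, not an actual one. It does not remove the point, because the refusal sentence is silent on timing and the only instruction to place the device comes after consent.

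A second reply is that matching on temperature at ANAPOD application handles much of the problem. Both devices are requested in one step, so the natural control equivalent would be temperature when forced air starts, and the list of criteria need not be exhaustive. That is a reasonable reading, and such matching may absorb part of a difference. But the protocol does not state it, and matching on temperature does not align time already spent on forced air.

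Third, flow sheets already record active warming methods. This also stands: in treated patients the data may be largely recoverable. However, no planned analysis or table uses start times.

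Finally, the same table of shifts could be drawn for any unmatched covariate in a historically controlled study. That is fair, and the table should not carry the argument. What makes forced-air timing specific is that the protocol places a consent step before it in one group only and itself names forced air as affecting the endpoint.

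**Conclusion.** The point holds as a correctable weakness in the design text. Followed as written, standard warming in treated patients waits for surrogate consent, controls had no such wait, and neither matching nor analysis addresses the difference. Any net difference would be read as an HHBC effect.

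A reader might infer that treated patients are in fact denied forced air until consent, or that the result is biased against HHBC by a known amount. The documents support neither: they give no consent delay, no forced-air start times in either group and no carry-through to the endpoint. The power and false-positive figures rest on assumed shifts, a two-sided t-test and the plan's SD of 1.3 h. Nor do the documents compare blanket types or settings, so those are not shown to be confounders.

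The change should be made because it is nearly free, removes a possible source of bias and ensures that standard care does not wait for research consent.

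**What to change.** 1. Amend Design & Procedures to say that forced air starts on CTICU admission for every hypothermic patient as usual care, and that only HHBC waits for consent.
2. Chart forced-air start and HHBC start in treated patients, extract forced-air start from control charts where available, and report these times by group with counts of missing values.
3. Define the same time zero for both groups. If it is CTICU admission, require each control to be still below normothermia at the elapsed time at which the matched treated patient began HHBC. Without this, a patient who rewarms before HHBC is connected cannot count as treated while a similar control still counts, which is guaranteed-time bias against HHBC; the plan expects some patients to be normothermic by 45 minutes. If HHBC start is preferred, state which moment represents it in controls.

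A sensitivity analysis restricted to patients with early charted forced air is not advised. With forced air started on admission, nearly all treated patients would qualify, so exclusions would fall mainly on controls and break the matched sets.

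The cost is a few protocol sentences, two charted times in treated patients, one in controls and one by-group table. The downsides are a little more chart extraction, some missing control start times and, if admission is time zero, a further condition on choosing controls.

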### **Data Analysis & Statistical Considerations**

Descriptive statistics will be used to evaluate patient demographics and clinical characteristics. Descriptive statistics will be summarized as mean  $\pm$  (SD) or median (interquartile range) for continuous variables and group frequencies (%) for dichotomous or categorical variables.

As all patients are expected to achieve normothermia within the study period, the primary outcome of time to normothermia will be analyzed as a numeric outcome variable. Following validation of distributional assumptions we will compare the time to normothermia between the two groups via t-test or Wilcoxon rank sum test as appropriate. It is expected that the patients will reach normothermia between 45 minutes and 6 hours after admission to the ICU.

By using a 2:1 matching ratio and a moderate level of variability (SD=1.3 hours) a study of 14 prospectively enrolled patients and 28 retrospectively matched patients would attain 82% power to detect a 1.25 hour difference between time to normothermia in the two groups at alpha level 0.05.

Secondary numeric outcomes such as time to extubation, time to normal PH, and coagulopathy lab values will be analyzed by t-test or Wilcoxon rank sum test as appropriate. Differences in categorical outcomes between treatment groups such as shivering will be analyzed via chi-square or fisher exact tests. As the patients will be matched on key confounders no further adjustment is expected to be necessary, so the moderate sample size should not limit the primary analysis. Potential subgroup analysis may be conducted in an exploratory analysis to determine if the treatment effect of ANAPOD warming is different by procedure type or patient/surgical characteristics.

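### The unadjusted comparison of clinician-timed coagulation values with historical controls cannot reliably separate an HHBC effect from coagulopathy already present at admission or from differences in sampling time

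*Combined protocol and SAP*

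**What the plan says.** *Purpose of the Study* sets the secondary aim: "assess whether use of HHBC shorten time to extubation, improve coagulopathy, decrease bleeding, and metabolic derangements seen with hypothermia".

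*Background & Significance* gives two sources of the coagulopathy. Cooling and rewarming during bypass "contributes to the post-procedural coagulopathy and physiologic perturbations". Separately, "After-drop may contribute to post-operative complications of hypothermia such as shivering, coagulopathy". The first source precedes ICU care; the second is one that ICU rewarming might influence. Neither is quantified.

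*Design & Procedures* starts HHBC after ICU admission and next-of-kin consent, when the provider will "ask the respiratory therapist to set up and connect a heated humidified breathing circuit". Core temperature is recorded every 15-30 minutes and chest tube output hourly. Laboratory tests have no study schedule: "Other patient management decisions (ie medication changes, laboratory assessments...etc) per direction of ICU providers". The comparator is a historical cohort warmed by forced air alone.

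*Selection of Subjects* (retrospective part) matches on temperature, type of surgery, BMI and deep hypothermic arrest. The only reference point defined is the temperature when ANAPOD is applied, an event that controls do not have.

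*Data Analysis & Statistical Considerations* says that "coagulopathy lab values will be analyzed by t-test or Wilcoxon rank sum test as appropriate". It names no assay, time point, baseline or rule for repeated panels, and states that matching should make further adjustment unnecessary.

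**The concern.** To improve coagulopathy is to change it after HHBC begins. A two-group comparison of values estimates that change only if the groups had similar coagulation status before HHBC and were sampled at comparable times. Randomisation would support the first condition and a sampling schedule the second; this design has neither. The stated expectation that no adjustment is needed makes this more than missing detail.

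A difference could then arise from coagulation status at admission, from when blood was drawn, from which patients were sampled, or from HHBC, and the planned test cannot tell these apart. It could credit HHBC with a benefit or harm it did not cause. If panels drawn before HHBC were counted as outcomes, it could also dilute a real effect.

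**Working it through.** **1. The plan's own figure.** Inputs from *Data Analysis & Statistical Considerations*: 14 and 28 patients, difference 1.25 h, SD 1.3 h, alpha 0.05 (sidedness not stated; two-sided assumed).
- Standard error in SD units: √(1/14 + 1/28) = 0.327.
- Noncentrality: 1.25 / (1.3 × 0.327) = 2.94, with 40 degrees of freedom.
- Power: 81.8% by noncentral t, 83.6% by normal approximation. One-sided versions give 89-90% and do not match.

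The stated 82% is reproduced. It concerns time to normothermia only; no figure is given for coagulation values.

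**2. What these numbers can detect for a coagulation value.** With no coagulation SD in the documents, results are in SD units. At 14 versus 28, two-sided 5%, an unadjusted comparison has 80% power for 0.94 SD and about 32% power for 0.5 SD.

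**3. Effect of a pre-existing difference.** Suppose the populations differ by b SD before HHBC, the baseline-to-outcome correlation is r, and HHBC does nothing. The outcome means then differ by r × b. With b = 0.5 (assumed), the unadjusted test rejects as follows:

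| r (assumed) | Shift r × b | Rejection rate (nominal 5%) |
|---|---|---|
| 0.5 | 0.25 SD | 12% |
| 0.7 | 0.35 SD | 18% |
| 0.9 | 0.45 SD | 27% |

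With b = 0.25 the rates are 7%, 8% and 10%; with b = 0.75 they are 20%, 35% and 52%. Here b is a systematic difference between cohorts. Chance imbalance alone is already covered by the 5%.

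**4. Effect of unequal sampling times.** If values drift by g SD per hour and mean sampling times differ by t hours, the spurious difference is g × t. For g = 0.2 and t = 2 (both assumed) it is 0.4 SD, and the test rejects about 22% of the time. For g = 0.1 and t = 1 the rate is 6%; for g = 0.3 and t = 3 it is 77%.

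**5. Dilution.** If a share p of values in both groups precedes HHBC, with the same timing mix, the expected mean difference is (1 − p) times the true one: half at p = 0.5 (assumed). This applies to means and does not carry over directly to a Wilcoxon test.

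**6. What baseline adjustment gains.** With the baseline as covariate, residual variance is 1 − r², so the detectable difference is about 0.94 × √(1 − r²):
- r = 0.5: 0.81 SD
- r = 0.7: 0.67 SD
- r = 0.9: 0.41 SD

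Under the linear model in step 3, adjustment also removes the r × b shift. It does nothing for the timing shift in step 4, which needs a common window.

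**The case against.** The strongest reply is that this is one of several secondary outcomes, carries no power claim, and is merely under-described. The analysis text does not say that levels rather than changes will be used, nor that admission panels will count as outcomes; it selects no panel at all. Matching on type of surgery and deep hypothermic arrest gives some control of bypass exposure, and a comparison of levels is biased only if the groups differ in prior status, sampling time or selection. Much of this stands: unadjusted levels are the natural reading but still an inference, and control is partial rather than absent. What does not stand is that the gap is harmless, because the plan expects no further adjustment while matching on neither coagulation status nor sampling time.

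A reader might also infer more than the documents support:
- *Bypass sets most of the coagulopathy.* The background says only that it contributes, and names afterdrop as another possible source.
- *Later panels are drawn mainly from bleeding or transfused patients.* The plan says only that providers decide; routine panels fit the text equally well.
- *Late values reflect time and transfusion more than warming.* Nothing in the plan ranks these.

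Two objections to the remedy also have force. A window does not remove selection by clinician ordering; it only makes it visible. And by 6 h the plan expects normothermia, at which point HHBC is discontinued, so the temperature contrast may have narrowed.

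**Conclusion.** The point holds in limited form. As planned, the coagulation comparison cannot reliably separate an HHBC effect from coagulopathy present at admission or from unequal sampling times. It would go too far to say that it can show nothing: if the cohorts happened to be alike in both respects, the comparison would not be biased by them.

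The size is unknown. The illustrated error rates, about 12% to 27% for a 0.5 SD baseline difference and about 22% for the timing example, rest wholly on assumed imbalance, correlation and drift. They show that modest differences would be enough to mislead, not that such differences exist. The change should be made, but it affects a secondary objective only.

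**What to change.** In *Data Analysis & Statistical Considerations*:
- Name the coagulation assays.
- Use the admission (last pre-HHBC) value only as baseline.
- Define the outcome as the value nearest a fixed time after ICU admission, within a pre-set window. An example is 4-8 h, centred on the plan's own 6 h upper limit for normothermia. Apply the same extraction rule to both cohorts.
- Compare groups with the baseline value as covariate.
- Report by group the share with a baseline value, the share with an in-window value, and the share given blood products beforehand.
- Label the result exploratory, because sampling remains clinician-ordered.

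As a supporting measure for the bleeding objective, compare cumulative chest tube output over the same early window from the hourly record, after checking that this record is complete in the historical controls. The plan prescribes hourly recording for study patients but does not describe the controls' charts.

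The cost is a change of wording and a chart-extraction rule, with no added samples. The real downside is that patients lacking either value drop out of this comparison. That matters with 14 treated patients, so the number must be shown. On precision alone, adjustment at r = 0.7 leaves 1 − 0.49 = 0.51 of the variance and would offset a loss of up to about half the patients. It would not correct for which patients were lost.

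### Time to 36.5 °C may be read at any of five core sites, and site is neither fixed within patient, matched nor analysed, so the primary outcome is open to a site-related bias of unknown size

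*Combined protocol and SAP*

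**What the plan says.** The primary outcome is time to normothermia, defined as 36.5 °C or above (Purpose of the Study). Design & Procedures sets the measurement: "Core temperature and location (esophageal, nasopharyngeal, bladder, rectal, blood) will be recorded every 15-30 minutes until normothermia reached". Site is therefore collected prospectively, but no site is required or preferred, none is ruled out, and nothing says that a patient stays on one site from start to threshold.

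The same section describes the treated patients: "Patients are intubated and sedated on admission to the CTICU after cardiac surgery". They receive the heated circuit plus forced air, and the investigators will "compare them with a historical cohort that has used forced air warming device only".

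The criteria for choosing controls, listed after Exclusion Criteria, cover forced-air-only hypothermic bypass patients, type of surgery, BMI, deep hypothermic arrest and a reference temperature: "Temp at time of ANAPOD application would be our reference point". Probe site is not among them.

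Data Analysis & Statistical Considerations will "compare the time to normothermia between the two groups via t-test or Wilcoxon rank sum test as appropriate" and adds "As the patients will be matched on key confounders no further adjustment is expected to be necessary". No analysis by site is planned.

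**The concern.** The endpoint is a threshold crossing on whichever probe a patient happens to have. Two routes to bias follow, and they behave differently.

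- **Local heating.** The intervention heats the airway gas, and two of the five permitted sites lie in or near the airway. If a probe there reads high because of the gas, it does so only in treated patients, and the crossing comes early without a matching gain in body heat. Matching on temperature when the circuit is applied does not remove this, because the circuit has not yet had time to act on the probe.
- **Site mix.** Controls come from another period and their sites may be distributed differently. Core sites need not agree or move together during rewarming, so an imbalance could push the comparison in either direction.

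If either effect is material, a positive result could not be read cleanly as faster rewarming.

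**Working it through.** **Inputs from the documents**
- 14 treated and 28 control patients, SD 1.3 h, target difference 1.25 h, alpha 0.05, stated power 82% (Data Analysis & Statistical Considerations, the sentence beginning "By using a 2:1 matching ratio and a moderate level of variability (SD=1.3 hours) a study of 14 prospectively enrolled patients").
- Rewarming rate from the cohort in Background & Significance, 34.7 to 38.3 °C over 8 h: (38.3 − 34.7)/8 = 0.45 °C/h on average. That section calls the curve sigmoid and steepest at 2 to 4 h, so the rate at crossing may be higher.

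**Inputs assumed, because the documents give none**
- Upward offset at an affected probe: 0.1 to 0.5 °C.
- Share of treated patients affected: a quarter, half or all.
- A faster rate of 0.9 °C/h (twice the average), as a milder case.

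**Step 1: reproduce the plan's power.** SE = 1.3 × √(1/14 + 1/28) = 0.4255 h. Noncentrality = 1.25/0.4255 = 2.94 on 40 degrees of freedom. The two-sided t-test has 81.8% power, matching the stated 82%; one-sided would be 89.3%. Sidedness is not stated, so two-sided is inferred. The sample-size statement is not at fault.

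**Step 2: convert an offset to hours.** Group shift = share × offset / rate. At 0.45 °C/h, each 0.1 °C brings one patient's crossing forward by 0.1/0.45 = 0.22 h, about 13 minutes, which is less than one 15-to-30-minute recording interval. To produce the whole 1.25 h unaided, every treated patient would need an offset of 1.25 × 0.45 = 0.56 °C.

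**Step 3: false-positive rate with no true effect.** Same t-test, with noncentrality = shift/0.4255.

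| Rate (°C/h) | Offset (°C) | Share affected | Shift (h) | % of 1.25 h | Two-sided rejection |
|---|---|---|---|---|---|
| 0.45 | 0.1 | half | 0.11 | 9 | 5.7% |
| 0.45 | 0.3 | quarter | 0.17 | 13 | 6.7% |
| 0.45 | 0.3 | half | 0.33 | 27 | 11.9% |
| 0.45 | 0.3 | all | 0.67 | 53 | 33.4% |
| 0.45 | 0.5 | half | 0.56 | 44 | 24.7% |
| 0.45 | 0.5 | all | 1.11 | 89 | 72.2% |
| 0.9 | 0.3 | half | 0.17 | 13 | 6.7% |
| 0.9 | 0.3 | all | 0.33 | 27 | 11.9% |
| 0.9 | 0.5 | all | 0.56 | 44 | 24.7% |

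**Step 4: check the shortcut.** When only half the patients are affected, the treated group is a mixture, which the formula ignores. Simulating the mixture at 0.45 °C/h (20,000 trials per case) gave 12.1% for 0.3 °C in half and 23.8% for 0.5 °C in half, close to the table.

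The table covers local heating only. The documents offer nothing from which to size, or even sign, a site-mix effect.

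**The case against.** The strongest reply is that the mechanism is nowhere in the documents. They do not say that circuit gas warms either probe, or how often those sites are used in this unit. Patients are intubated, so the gas travels through the tube and may largely bypass the nasopharynx. That weakens the path for one of the two suspect sites and makes the size at the other uncertain. This stands. So does the observation that mild inputs leave the error rate at 5.7% to 6.7%, and that a faster rate at crossing halves every shift.

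A reader might infer that the plan's bias is known to favour HHBC. The documents do not support that: only local heating has a fixed direction, and it is a possibility rather than a finding; a differing site mix could go either way. A reader might also infer that matching on site would cure the problem. It would not, because a control with an esophageal probe is still breathing unheated gas. Nor is the choice of an unadjusted test the root of it, since covariate adjustment alone could not separate a warmed probe from a warmed patient.

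None of this answers the narrower point: the plan leaves the measurement site of its primary endpoint open in a comparison where only one group has its airway gas heated.

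**Conclusion.** The point holds as a gap in how the endpoint is measured, with a plausible but unquantified bias. What rests on the documents is that five sites are allowed, no fixed-site rule exists, and site enters neither matching nor analysis. What rests on assumption is any offset, the share of patients affected and the rate at crossing. Across those assumptions the false-positive rate runs from about nominal to 72%. The upper end needs 0.5 °C in every treated patient at the slower rate and should not be quoted as an expected value. The change is worth making because it is cheap before controls are chosen, and a positive result would otherwise be hard to defend.

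**What to change.** In Design & Procedures and in Data Analysis & Statistical Considerations, state the following:

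1. For the primary endpoint, each patient's temperature is read from one site, the same from time zero to 36.5 °C. A charted bladder, rectal or blood reading is used where available, by the same rule in both groups.
2. A sensitivity analysis of the primary outcome excludes patients who have only nasopharyngeal or esophageal readings.
3. Site is reported by group. Balancing site when selecting controls is useful against ordinary between-site differences, but should not be presented as protection against local heating in the HHBC group.

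One consequence needs wording. Frequent recording ends at normothermia, and the plan says "Alert Respiratory therapy once normothermia (36.5 °C) has been achieved for discontinuation of HHBC". If the bedside reading and the endpoint reading come from different sites, the plan should make clear that frequent recording of the endpoint site continues until that site crosses, and which reading the discontinuation instruction refers to.

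Costs: mostly wording, since site is already recorded prospectively. The documents do not confirm that site, or a non-airway reading, can be retrieved from historical charts, so this should be checked before controls are selected. The control pool may shrink, and the sensitivity analysis may leave few of the 14 treated patients, so it would be supportive rather than decisive. Study patients have a lower body forced-air device while the controls' blanket type is not stated; it should be recorded alongside site when bladder or rectal readings are used.
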